4 STUDY PARAMETERS

4.1 Participant Disposition

Participants who completed the Day 84 visit will be considered as having reached Study Completion, otherwise, they will be classified in the Study Discontinuation group.

Reason(s) for discontinuation will be recorded and could include the following:

- Withdrawal of consent
- Administrative decision by the investigator or Sponsor
- Significant protocol deviation
- Participant noncompliance, or other significant protocol deviation

- Safety concern by the investigator or Sponsor
- Lost to follow-up

Time in the study will be computed as following:

Time in Study (Study duration) = Last Date in study – Date of First Dose + 1

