#### 6.4 STUDY INTERVENTION COMPLIANCE

Participants who are inadvertently enrolled, despite significant deviation from protocol-specified inclusion/exclusion criteria, will be discontinued from participation in the study. Participants will be scheduled for follow-up visits and followed for 8 weeks post-treatment for safety per protocol.

At each post-baseline visit, participants will be questioned as to concomitant medications, as well as exclusionary criteria to ensure protocol compliance. Urine drug screens will be performed during the screening visit (Day -14 to Day -2), at the Days 7 (if conducted in-clinic), 28, and 84 visits for all participants. Dosing compliance will be assessed when the participant returns the study drug (both bottles) to the investigator, at which time the study drug bottles will be weighed.

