## 7 STUDY INTERVENTION DISCONTINUATION AND PARTICIPANT DISCONTINUATION/WITHDRAWAL

### 7.1 DISCONTINUATION OF STUDY INTERVENTION

The investigator may discontinue the study drug at any time if there is a safety concern. If the study drug is discontinued, then the participant will early exit from the study. If the participant has discontinued the study drug because of an SAE related to the study drug, that participant should be monitored for at least 30 days or until the SAE has resolved or stabilized.

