### 7.2 PARTICIPANT DISCONTINUATION/WITHDRAWAL FROM THE STUDY

Participants are free to discontinue the study at any time, for any reason, and without prejudice to further treatment. The investigator may remove a participant if, in the investigator's judgment, continued participation would pose unacceptable risk to the participant or to the integrity of the study data. Reasons for removal or withdrawal might include:

- Withdrawal of consent
- Administrative decision by the investigator or Sponsor
- Significant protocol deviation
- Participant noncompliance, or other significant protocol deviation
- Safety concern by the investigator or Sponsor
- Lost to follow-up

With the exception of withdrawal of consent, participant withdrawal should be discussed with the Medical Monitor, when possible, prior to withdrawing. Notification of early participant discontinuation from the study and the reason for discontinuation will be made to Allgenesis and will be clearly documented on the appropriate eCRF. If a participant discontinues prior to completing the study, the procedures outlined for the Exit visit should be performed at the last visit the participant attends.

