5.3 Modified Intent-to-Treat Population

The modified intent-to-treat (mITT) population will include all randomized participants who receive at least one dose of study eye drop and had conjunctival hyperemia evaluated at both the Day 1 and Day 28 visits. This is the efficacy population. Results will be presented by the treatment assigned during randomization.

The primary efficacy analyses will be conducted using the mITT population.

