5.4 Per Protocol Population

The per-protocol (PP) population will consist of all participants in the mITT population who do not have major protocol deviations considered to affect the primary efficacy variable, have been at least 70% compliant with the study treatment according to participant dosing diary AND have been administered IP according to protocol at least 4 of the 6 doses immediately prior to that study visit.

The rules for determining exclusion from the per-protocol population will be made and implemented prior to database lock.

Sensitivity analyses of the primary efficacy analyses will be conducted using the PP population.

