6 STATISTICAL METHODS

All data processing, summarization, and analyses will be performed using SAS® Version 9.4 or higher.

Unless otherwise specified, for continuous variables, descriptive statistics will include the number of participants/eyes (n), mean, standard deviation, median, minimum and maximum values. Categorical variables will be summarized using frequency and percentages.

Unless, otherwise stated, missing data will be handled as is, except when the aforementioned dates are required for calculations, the partial dates will have either '01' or 'Jan' imputed with an exception for dates related to AEs where the date closest to the last event (screening, first dose, last dose, etc.) should be used rather than arbitrary '01' of that month.

All efficacy data will be summarized by treatment group and time point using appropriate descriptive statistics. Summaries will be presented for both the mITT and PP populations. Due to the small number of participants that are expected to be enrolled at each center, all summaries and analyses will be performed using data pooled across centers.

Baseline results will be those recorded prior to dosing. In cases where more than one pre-dose observation has been recorded, the **last recording** will be identified as the baseline result.

Study days will be numbered relative to the date of the first dosing. The start of study (Day 1) will be defined as the date on which a participant takes the first dose of any study medication, as recorded on the CRF. Relative to study start, days will be numbered ...-2, -1, 1, 2, ... with Day - 1 being the day prior to the start of study medication (Pre-Dose).

Recorded data will be assigned to evaluation/assessment windows. If more than one clinical evaluation is made within a window for a particular visit, the record with the date closest to the targeted window will be used except for AEs where the **worst assessment** will be used.

Visit windows and analytical windows are defined as follow:

Visit	Targeted Window	Analytical Window
Pre-dose (Screening)	Day -14 to Day -1	Day -18 to Day -1
Visit 1 (First dosing date)	Day 1	Day 1
Visit 2 (optional)	Day 7 (± 3 day)	Day 2 to Day 16
Visit 3 (End of treatment visit)	Day 28 (± 3 days)	Day 17 to 3 days after the last dose and up to Day 42
Visit 4	Day 56 (± 5 days)	Day 43 to Day 70
Visit 5 (End of study visit)	Day 84 (± 5 days)	Day 71 to End of Study

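### Participants removed for noncompliance or a deviation before a Day 28 photograph leave both mITT and per-protocol sets, so the per-protocol analysis cannot show the effect of that selection

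*SAP*

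**What the plan says.** **Removal.** Protocol 7.2 allows the investigator to remove a participant when "continued participation would pose unacceptable risk to the participant or to the integrity of the study data". Its examples include significant deviation and noncompliance. SAP 4.1 repeats the list as reasons to be recorded, with "Participant noncompliance, or other significant protocol deviation" as one entry. Protocol 6.4 is firmer for people enrolled despite significant eligibility deviations: they "will be discontinued from participation in the study". Its next sentence schedules follow-up visits for them over 8 weeks, for safety. Protocol 7.1 adds: "If the study drug is discontinued, then the participant will early exit from the study".

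**Analysis sets.** SAP 5.3 limits mITT to dosed, randomized participants who "had conjunctival hyperemia evaluated at both the Day 1 and Day 28 visits". SAP 5.4 builds PP from mITT members who "do not have major protocol deviations considered to affect the primary efficacy variable" and who also meet the diary rules (70% overall and 4 of the last 6 doses). SAP 6.5 bases all efficacy analyses on mITT, and SAP 6.5.3 names PP as the sensitivity analysis. SAP 5.1 defines an intent-to-treat set, but no efficacy analysis is assigned to it. Protocol 9.3 rules out imputation.

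**Exit data.** SAP 6.2.3 maps efficacy data from a treatment-discontinuation exit to the next scheduled visit and treats them as observed. The Day 28 analysis window in SAP 6 is "Day 17 to 3 days after the last dose and up to Day 42". Protocol 7.2 has early leavers undergo the Exit-visit procedures.

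**The concern.** Noncompliance and deviations can act at two points. One is the PP definition, where such exclusions belong. The other is removal from the study, which can also take the participant out of the primary analysis set. Removal is a decision made after randomization and may be related to outcome.

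A PP analysis is informative as a check on mITT only if mITT still contains the people PP leaves out. If some are already gone from both sets, agreement between the two results is weaker evidence of robustness than it appears. If those removed would have done worse than those kept, the mITT estimate moves toward the effect in participants who dosed well.

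**Working it through.** **1. Who is lost.** Removal before a Day 28 grade means the mITT condition in SAP 5.3 fails. Because PP is a subset of mITT, PP fails too. With no imputation, nothing restores the participant. Running the Appendix 2 model on the intent-to-treat set would not help by itself, since a participant with no Day 28 change contributes no response.

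**2. Whether the SAP's provisions rescue them.**
- A participant removed at or after the Day 28 photograph stays in mITT.
- An exit photograph from Day 17 onward could fall in the Day 28 window, and one taken after Day 7 but before Day 28 could be mapped to Day 28. An exit before Day 7 would map to Day 7.
- All of this needs a photograph. The Day 84/Exit assessments in protocol 1.2 list visual acuity, pressure, biomicroscopy, ophthalmoscopy and two optional tests. In the protocol 1.3 table, the ocular photography row is blank at Day 84. The mapping rule therefore usually has no reading-center grade to map.

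**3. How wide the route is.** Day 7 is a phone call by default. Bottles are weighed there only if the visit is in clinic, and otherwise at Day 28 (protocol 1.3, footnote b). Noncompliance will therefore mostly be established at the visit where the primary photograph is taken. Earlier detection remains possible through an in-clinic Day 7 visit, unscheduled visits (protocol 6.1.2) and the questioning on medications and exclusion criteria at each post-baseline visit (protocol 6.4).

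**4. The plan's own figures.** Protocol 9.2 gives SD 1.0, difference 1, 20 per group and at least 90% power. For an overall one-way F-test with group means (0, 0, 1), the noncentrality is 20 × [(1/3)² + (1/3)² + (2/3)²] = 13.3. With 2 and 57 degrees of freedom the power is 0.8997, so the stated figure reproduces. Enrolling 70 for 60 evaluable implies a loss of 10/70 = 14.3% from all causes. No rate is given for removal due to noncompliance or deviation.

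**5. Illustrative bias.** Let a fraction q of one arm be removed, and let their mean change differ by g from that of the participants retained. The retained mean then differs from the full-arm mean by q × g. Both q and g are assumptions; the upper q attributes the whole 14.3% allowance to this cause.

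| q | g = 0.25 | g = 0.5 | g = 1.0 |
|---|---|---|---|
| 5% | 0.013 | 0.025 | 0.050 |
| 10% | 0.025 | 0.050 | 0.100 |
| 14.3% | 0.036 | 0.071 | 0.143 |

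These are points on the hyperemia scale, against a design difference of 1. If both comparison arms lose participants with the same g, the bias in the contrast is the difference in q multiplied by g, so equal removal cancels.

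**6. Effect on one test.** With 20 per arm and SD 1, the standard error of a pairwise difference is √(2/20) = 0.316. Under no true effect, a bias of 0.071 raises the two-sided error of a single 5% t-test (38 degrees of freedom) to about 0.056. A bias of 0.143 raises it to about 0.073.

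**The case against.** **Removal is not automatic.** SAP 4.1 is a list of recorded reasons, not a removal rule. Protocol 7.2 is permissive and asks for discussion with the Medical Monitor where possible. This stands: a reader might infer that the plan itself expels noncompliers, but for noncompliance the documents only allow it. The one mandatory removal, in protocol 6.4, concerns eligibility rather than dosing behaviour.

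**Most noncompliers will have a Day 28 grade.** This also stands. They remain in mITT and drop only from PP, so the mITT and PP comparison keeps some value. It would be too strong to say that it tells the reader nothing.

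**Removal by arm.** A reader might infer that it will differ because active drops are yellowish and vehicle is clear. The documents do not establish that. Protocol 6.3 restricts kit access, tells participants not to describe the drops and has the unmasked administrator collect and weigh the bottles at Day 28. SAP 3.4 masks investigators. Protocol 6.4 does speak of bottles being returned to the investigator, so exposure to colour is possible, but it is conjecture.

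**Exclusions will be visible.** SAP 6.1 tabulates exclusions from efficacy, with reasons, by assigned group. That shows how many were lost and why, but not what their loss did to the estimate.

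**The wider issue is mITT itself.** Conditioning on Day 28 data affects every cause of loss, and this point covers only one. That is fair. It is, however, the part of the loss that sponsor and sites control, since these people may be willing to attend.

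**Conclusion.** The concern holds in a limited form. Removal for noncompliance (permitted) or significant ineligibility (required) before a Day 28 grade takes the participant out of mITT and PP together, and PP cannot reveal the effect. The exit-mapping rule does not generally prevent this, because no photograph is scheduled at early exit.

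The route is probably narrow and the size is unknown. The range of about 0.01 to 0.14 points assumes 5% to 14% removal confined to one arm and a gap of 0.25 to 1.0 points.

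A reader might go further and put the overstatement at 10% to 15%, from 23/21 = 1.095 or 23/20 = 1.15. The documents do not support this. It needs every removed participant to have had no benefit and no offset in the vehicle arm. The planned loss is 10/3 = 3.3 per arm for all causes, so three removals would use about 90% of that allowance.

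A wording change is justified because it costs little and removes an avoidable selection. The trial's conclusions do not turn on it.

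**What to change.** 1. **Protocol 7.2:** state that noncompliance or a protocol deviation without a safety concern is not by itself a reason to end study visits. Keep these participants in scheduled visits through the Day 28 photograph and follow-up. This concerns data collection only; whether dosing continues is a separate decision. Protocol 7.1 and SAP 6.2.3, which tie stopping drug to leaving the study, must be made consistent with the new sentence.
2. **SAP 5.3 and 5.4:** analyse these participants in mITT as randomized, and apply noncompliance and deviation exclusions only to PP. Check the Day 28 window as well: its limit of 3 days after the last dose could exclude a Day 28 photograph taken after dosing had stopped.
3. **SAP 4.1:** keep the reason codes, so that any exits that still occur are reported.
4. **Protocol 6.4:** reconcile discontinuation from participation with the follow-up visits scheduled in the next sentence, and say whether the Day 28 photograph is taken.
5. **SAP 6.2.3 and protocol 7.2, 1.2 and 1.3:** reconcile the mapping of exit efficacy data with exit procedures that list no ocular photography.

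**Cost:** short wording changes in both documents and a few visits already in the schedule. The mITT estimate may come out slightly smaller. Losses from withdrawn consent, safety exits and lost contact are not addressed by this change.

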4.2 Study Treatment Group

For safety and PK analysis, participants will be grouped based on the treatment actually received.

For efficacy analysis, it will be based on the treatment assigned per randomization, even it differs from the treatment actually received.

4.3 Primary Efficacy Endpoints

The primary efficacy measure is the overall conjunctival hyperemia score graded by the masked reading center and defined as the average of the scores of each quadrant. The primary efficacy endpoint is the change from baseline in overall conjunctival hyperemia score at Day 28.

The primary efficacy analysis will be based on the modified intent-to-treat (mITT) population.

4.4 Secondary Efficacy Endpoints

Secondary endpoints include:

- Change from baseline in conjunctival hyperemia score in the study quadrant at Day 28

4.5 Exploratory Efficacy Endpoints

Exploratory efficacy endpoints include:

- Change from baseline in pterygium vascularity at Days 28 and 56
- Change from baseline in pterygium volume (in selected sites only) at Days 28 and 56
- Change from baseline in pterygium vessel length at Days 28 and 56

4.6 Pharmacokinetic Endpoints (if available)

Data on plasma drug concentrations, if available, will be collected for those participating in the sub-study. Pharmacokinetic endpoints include:

- Individual and mean concentration and standard deviation for Day 1, Day 28, and Day 56
- Partial Area Under the Curve (AUC_{0-1h}) on Day 1 and Day 28

4.7 Safety Endpoints

The Medical Dictionary for Regulatory Activities nomenclature (MedDRA V21.0 at time of SAP publication, or the current version when superseded) will be used to code AEs.

Treatment-emergent AEs are any AEs with an onset date equal to or after the date of the first dose and **within 3 days** after the last dose of the study eye drop. A pre-existing event that worsens after the first dose date is considered a treatment emergent event. Treatment-related AEs are any AEs with a relationship of unlikely related, possibly related or related to study medication, or AEs with a missing relationship.

Safety endpoints include:

- Adverse events
- Concomitant medications
- Concurrent procedures
- Vital signs
- Laboratory tests (urinalysis, hematology, and serum chemistry parameters)
- Electrocardiogram
- Best-corrected visual acuity
- Intraocular pressure using a Goldmann applanation tonometer
- Biomicroscopy
- Tear film break-up time
- Lissamine green conjunctival staining
- Ophthalmoscopy

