#### 8.3.5 RELATIONSHIP TO STUDY INTERVENTION

A determination will be made of the relationship (if any) between an AE and the study drug. A causal relationship is present if a determination is made that there is a reasonable possibility that the AE may have been caused by the drug.

- **Not related:** A causal relationship can be excluded and another documented cause of the AE is most plausible
- **Unlikely related:** A causal relationship is improbable and another documented cause of the AE is most plausible
- **Possibly related:** A causal relationship is clinically/biologically plausible and there is a plausible time sequence between onset of the AE and administration of the study drug
- **Related:** A causal relationship is clinically/biologically highly plausible, there is a plausible time sequence between onset of the AE and administration of the study drug, and there is a reasonable response on withdrawal

---

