6.6.1 Adverse Events

All AEs reported during the study period will be recorded and coded using MedDRA terminology (MedDRA V21.0 at time of SAP publication, or the current version when superseded). An AE will be considered as treatment-emergent adverse event (TEAE) if it has an onset during the treatment period. A pre-existing event that worsens after the first dose date and within 3 days after the last dose date is considered a treatment emergent event.

The incidence of all TEAEs will be summarized using system organ class and preferred term by treatment group and overall. Adverse events will also be presented by relationship and severity. Further, serious adverse events and those events leading to discontinuation will also be presented.

Participants may have more than one AE per system organ class and preferred term. At each level of participant summarization, a participant will be counted once if they reported 1 or more events and will be reported with the highest severity. In cases where severity or relationship is missing, the most conservative approach will be taken (i.e. highest severity and assumed to be related).

The following overall summary will be presented by treatment and overall:

- Total number and percent of participants with
 - All AEs
 - Mild AEs
 - Moderate AEs
 - Severe AEs
 - Not related AE
 - Related AE
 - AE leading to death
 - AE leading to treatment discontinuation

- Total number and percent of participants with SAE
 - Mild SAE
 - Moderate SAE
 - Severe SAE
 - Not related SAE
 - Related SAE
 - SAE leading to Death
 - SAE leading to treatment discontinuation

The following summary tables of AEs will be presented by treatment and overall:

- Total number and percent of participants with AEs
 - By system organ and preferred term
 - By frequency for SAEs

- Total number and percent of participants treatment-related AEs
 - By preferred term and severity

The number and percent of participants with significant vital sign and laboratory findings during study will be summarized by group and overall.

The number and percent of participants with the following special interest events will be summarized by group and overall.

- Abnormal liver function (as defined in section 4.7.1)
- Ocular events

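### The SAP sets two different limits for counting a worsened pre-existing event as treatment-emergent, and its pooling of *unlikely related* with treatment-related is wider than the protocol's causality test

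*SAP*

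**What the plan says.** **Treatment-emergent events.** SAP 4.7 gives new events a closed window, from the first dose to 3 days after the last. For existing conditions it says only: "A pre-existing event that worsens after the first dose date is considered a treatment emergent event". SAP 6.6.1 restates both rules differently. A new event must begin in the treatment period, with no 3-day extension mentioned, and a pre-existing event counts if it "worsens after the first dose date and within 3 days after the last dose date". SAP 4.7.1 places events 3 days after the last dose in a separate post-treatment tabulation. Protocol 9.4.4 uses the term treatment-emergent without giving a window.

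**Relatedness.** Protocol 8.3.5 finds a causal relationship present when "there is a reasonable possibility that the AE may have been caused by the drug". It defines *unlikely related* as: "A causal relationship is improbable and another documented cause of the AE is most plausible". SAP 4.7 pools that category with the others: "Treatment-related AEs are any AEs with a relationship of unlikely related, possibly related or related to study medication". It adds events whose relationship is missing. SAP 6.6.1 asks for an overview with one row for related and one for not related events, without saying where the two middle categories go. It also asks for a table described as "Total number and percent of participants treatment-related AEs".

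**The concern.** Safety comes first among the trial's hypotheses (Protocol 4.1) and is to be judged by the incidence and severity of adverse events against vehicle. SAP 6.6 bases that judgement on treatment-emergent events, so the rule deciding which events qualify should exist once.

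As written, a programmer following SAP 4.7 and one following SAP 6.6.1 would classify the same late worsening differently. The double programming in SAP section 9 could expose the mismatch, but the SAP offers nothing to settle it. Timing adds to the problem. SAP 3.4 and section 8 plan a presentation of Day 28 results by unmasked treatment group, including safety to date, before the final lock. A rule left open until then could be chosen with group-level results in view.

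On relatedness, an event the protocol regards as improbably caused by the drug enters the treatment-related table, and the overview rows do not say which grouping they use.

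**Working it through.** The plan states no figure on this point, so there is none to reproduce. The check compares definitions and adds simple day arithmetic.

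**Inputs**
- Last dose: Day 28, visit window ±3 days (Protocol 1.3).
- End of adverse event collection: Day 84 (Protocol 8.3.7), visit window ±5 days (Protocol 1.3).
- Extension after last dose: 3 days (SAP 4.7 and 6.6.1).
- Early experience: 24 participants dosed and 9 adverse events, of which 7 unrelated, 1 possibly related and 1 related (Protocol 2.2).

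**Step 1: the worsening window**
- SAP 6.6.1 closes on Day 28 + 3 = Day 31.
- SAP 4.7 has no limit, so it runs to the end of collection, Day 84.
- Gap: 84 − 31 = 53 days (Days 32 to 84). The longer window is 84 / 31 = 2.7 times the shorter.
- Smallest gap within the visit windows: 79 − (31 + 3) = 45 days. Largest: 89 − (25 + 3) = 61 days.

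These figures apply to participants who complete treatment. Under Protocol 7.1, stopping the drug leads to early exit, so little follow-up would be affected in those participants.

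**Step 2: the same event under each section (last dose Day 28)**

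| Event | SAP 4.7 | SAP 6.6.1 | SAP 4.7.1 |
|---|---|---|---|
| Worsening, Days 32–84 | treatment-emergent | not treatment-emergent | can fall in post-treatment |
| New onset, Days 29–31 | treatment-emergent | not, if read literally | boundary at 3 days after last dose |

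For example, a condition present at screening that worsens on Day 56, which is 56 − 28 = 28 days after the last dose, is treatment-emergent under 4.7, not under 6.6.1, and post-treatment under 4.7.1. With one window in both sections the gap is 0.

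**Step 3: relatedness**
- The 9 early events add up: 7 + 1 + 1 = 9.
- Protocol test (possibly related plus related): 1 + 1 = 2 of 9, or 22.2%.
- SAP 4.7: 2 + u of 9, where u is the number of the 7 unrelated events that were graded *unlikely related*. The documents do not give u. From u = 0 to u = 7, the range is 2 of 9 (22.2%) to 9 of 9 (100%).

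That range shows what is unknown and is not an estimate. The early events are also not reported by arm.

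**The case against.** The best defence of the worsening rule is that SAP 4.7 intends the 3-day limit in its preceding sentence to carry over, and that 6.6.1 spells this out. That is probably the intent, but 4.7 does not say it, so the contradiction in the text stands. The defence is stronger on new onset. The window in 4.7, the 3-day limit in the next sentence of 6.6.1 and the post-treatment boundary in 4.7.1 all point to last dose plus 3 days, which makes *treatment period* in 6.6.1 look like loose wording. A late worsening would also still be recorded and listed with its dates, so nothing would be hidden.

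On relatedness, three points carry weight. Only the *not related* category in Protocol 8.3.5 treats causality as excluded, so pooling everything else is a conservative choice that cannot conceal a related event. Protocol 8.3.5 does not say how categories are to be pooled in tables. The four levels are collected (SAP 3.7), and tables by relationship are planned (SAP 4.7.1 and 6.6.1), so *unlikely related* events may already be separable in the outputs. What remains is the mismatch with the reasonable-possibility test, which SAP 1.1 does not list among its changes, and the undefined overview rows.

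A reader might infer that the related count changes with the SAP section used. The documents do not support that. SAP 6.6.1 contains no competing grouping, its treatment-related table uses the term defined in 4.7, and the two sections agree that a missing relationship counts as related (6.6.1: "In cases where severity or relationship is missing, the most conservative approach will be taken"). A reader might also infer a measurable dilution of the drug-versus-vehicle contrast. No document gives the frequency of *unlikely related* events in any arm, and the safety sections plan counts and percentages, not a risk ratio. Adding the same share of participants to both arms would leave the risk difference unchanged.

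**Conclusion.** The worsening rule is a genuine contradiction within the SAP. It affects any pre-existing event that worsens on Days 32 to 84, a span of 53 days (45 to 61 across the visit windows), assuming a last dose at the Day 28 visit and collection to the final visit. The span is the length of a window, not an effect size. The number of such events is not given and may be small.

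This limb does not contradict the protocol, which sets no treatment-emergent window. The conflict with the protocol concerns relatedness alone, and there it is a secondary matter: a conservative pooling that departs from the protocol's causality test without explanation, plus overview rows that need a definition. The shift in either count cannot be computed from the documents. The primary efficacy analysis is unaffected. This is a minor correction, worth making because safety conclusions rest on these counts.

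**What to change.** 1. In SAP 4.7 and 6.6.1, state one rule: an event is treatment-emergent if its onset or worsening falls from the first dose to 3 days after the last dose. Replace the treatment-period wording in 6.6.1 with that window.
2. In SAP 4.7.1, start the post-treatment category after that window closes, so that no event falls in both.
3. In SAP 6.6.1, define the related overview row as possibly related, related or missing, and the not related row as the rest. Show *unlikely related* on its own row so that the broader count stays visible. Bring the definition in 4.7 into line, or keep the wider pool there with a stated reason and a distinct label. Because a participant can have events in more than one category, a footnote should say that the rows do not add up.
4. Make these changes before the first database lock.

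The cost is a few lines of SAP text and matching table shells, with no new data. The main related count becomes less inclusive, which the extra row offsets. Late worsenings move to the post-treatment table and are still reported.
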